## List of Abbreviations

**BSS:** Balanced Salts Solution

**CV:** Coefficient of Variation

**ECD:** Endothelial cells density

**ICL:** Implantable Collamer Lens

**IOP:** Intra-Ocular Pressure

**OVD:** Ophthalmic Viscosurgical Device

**PIOL:** Phakic Intra-Ocular Lens

## 1 Background

Refractive errors (myopia, hyperopia and astigmatism) are quite prevalent worldwide, they constitute the most common cause of visual impairment with myopia in particular being progressively increasing in its prevalence so that it is predicted that by 2050 nearly half of the world population will be myopic. Management modalities include correction with glasses, contact lenses, laser vision correction, intracorneal implants and intraocular refractive procedures such as phakic intraocular lens (PIOL) implantation which involves the use of implantable collamer lens (ICL) in many cases. PIOLs are being extensively used since they preserve the integrity of the cornea and thereby attaining higher quality of vision compared with conventional kerato-refractive procedures. Furthermore; they allow broader range of refractive errors to be corrected. The Staar V4c EVO visian ICL (Staar surgical Inc, Lake Forest, CA, USA) has demonstrated effectiveness and an excellent safety profile with more than one million ICL implants had already been performed globally. However, complications such as raised intraocular pressure (IOP), cataract and pupillary block do happen. The ICL implantation procedure typically utilizes viscoelastics to facilitate introduction and positioning of the implant. Viscoelastics should be removed thoroughly at the conclusion of the procedure, and failure to do so may induce early postoperative IOP rise. It is logical to assume that viscoelastics use during surgery increases operation cost and time due to the extra steps involving the injection and removal of the substance. Increased manipulation during ICL implantation surgery and irrigation required to ensure adequate removal of viscoelastics may encourage cataract formation as well. Few studies investigated the safety and efficacy of ICL implantation without the use of viscoelastics, where they implemented balanced salt solution (BSS) instead as a novel technique. In the present study we retrospectively investigated the safety and efficacy of modifying ICL implantation technique by using cohesive OVD only without using dispersive OVDs.

## 2 Aim(s) / Objective (s)

Is omitting dispersive viscoelastic from the standard surgical technique and utilizing only cohesive OVDs (in what we call it reduced- OVD technique) safe and suitable?

## 3 Study Design and Methodology

### 3.1 Study Overview

This is a retrospective cross-sectional comparative study.

Data from private hospital records were accessed and analysed retrospectively.

### 3.2 Study Setting / Location

The study participants were all from Al-Ferdos private hospital in Baghdad, Iraq.

### 3.3 Study Population

All refractive surgery candidates attending the above hospital for the purpose of phakic introcular lens implantation were included in the study. However, the initial group allocation occurred before the commencement of the study on the basis of surgeon and patient preference, thereby, randomization was on convenient basis.

#### 3.3.1.1 Eligibility Criteria

To be eligible for enrolment into the study all of the inclusion criteria must be met. A participant will be excluded from the study if any of the exclusion criteria is present.

### **Inclusion Criteria**

Refractive surgery candidates

Aged from 18-55 years

Phakic intraocular lens implantation was performed (ICL type)

Committing to at least one preoperative visit for baseline assessment and multiple postoperative visits (at least 2 visits within a year) for follow-up assessment.

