## **3.6 Data collection and analysis**

Data will be collected by study co-investigators with assistance from IT personnel at the respective hospital from patients records that were identified as eligible for the study according to the inclusion criteria above. According to their data, participants will be split into two groups:

1- Traditional OVD group

In this group of patients, the ICL was implanted utilizing both cohesive and dispersive ophthalmic viscosurgical device.

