## 2- Reduced OVD group

In this group of patients, the ICL was implanted with the use of cohesive OVD only.

There is one primary outcome of interest which is the unaided visual acuity after the surgery, and several secondary outcomes including postoperative intraocular pressure, corneal specular microscopy parameters (ECD, CV and hexagonality), and the observed adverse events that can happen during the operation or postoperatively.

Data will then be stored electronically in a sheet format to enable for later statistical analysis.

Data collection was started at the conduct of the study in March 2024, and it is expected to be completed 3-4 months later.

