## 6 Study Impact and Significance

Traditionally dispersive OVDs has been used extensively during loading and implantation steps of ICL surgery. Reducing both the amount and the types of viscoelastics used (cohesive only) might potentially reduce cost and time of the procedure and might provide a substitute for safety studies regarding omitting or further reduction of cohesive OVDs and utilizing BSS only which carries lower risk of raised IOP and lower cost of the procedure.

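### The cohort is limited to completed ICL implantations, so operations started but ended without an implant are counted in neither group and failure per attempted operation cannot be estimated

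*Combined protocol and SAP*

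**What the plan says.** Section 3.3 (Study Population) is broad: "All refractive surgery candidates attending the above hospital for the purpose of phakic introcular lens implantation were included in the study". The Eligibility Criteria then narrow it. Section 3.3.1.1 states "To be eligible for enrolment into the study all of the inclusion criteria must be met", and one of the Inclusion Criteria is "Phakic intraocular lens implantation was performed (ICL type".

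The group definitions in section 3.6 repeat the condition. In the traditional group "the ICL was implanted utilizing both cohesive and dispersive ophthalmic viscosurgical device"; in the reduced group "the ICL was implanted with the use of cohesive OVD only".

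Section 3.6 also lists, among the secondary outcomes, "the observed adverse events that can happen during the operation or postoperatively". Section 6 says where the omitted product is normally used: "Traditionally dispersive OVDs has been used extensively during loading and implantation steps of ICL surgery". Section 2 asks whether leaving it out is safe and suitable.

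Two further rules bear on the point. The Inclusion Criteria require at least two postoperative visits within a year. Section 3.7, with the Exclusion Criteria, removes a participant altogether if any item listed in section 3.5 is missing. No section mentions an operation that was started and not completed.

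**The concern.** Whether a lens ends up in the eye is known only after the technique has been applied. Making it a condition of entry selects on an event that follows the intervention. The two techniques differ in the product used, and by the protocol's own account that product is used at loading and implantation. The comparison is therefore conditioned on success at the steps that were changed.

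What is at stake is the intraoperative part of the adverse-event outcome. Its proper denominator is operations attempted; the plan supplies operations completed. An operation that fails outright drops out of both numerator and denominator, although it bears directly on whether a technique is suitable. If such operations are unequally distributed between the groups, the comparison of adverse events is distorted, and the data as planned could not show it.

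**Working it through.** **Step 1. Trace one case through the plan.** Take an operation begun with cohesive OVD only and ended with no lens in the eye.

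- Section 3.3: included, because the patient came for implantation.
- Inclusion Criteria, implantation performed: not met on the natural reading, and section 3.3.1.1 makes each criterion mandatory.
- Section 3.6, group definitions: fits neither group, because both presuppose an implanted lens.
- Inclusion Criteria, two postoperative visits: may well fail.
- Section 3.7, complete data: excluded if any section 3.5 item is missing.

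Section 3.3 thus conflicts with the listed criteria. The case is removed by the criterion, again by the group definitions, and possibly by the visit and data rules. Correcting any one of these alone would not bring it back.

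**Step 2. What remains countable.** A lens that was damaged and replaced, inverted and repositioned, or withdrawn and later implanted still meets the criterion. Section 3.5 collects operative notes and surgical steps, and section 3.6 counts intraoperative events. Such cases are counted, subject to the visit and complete-data rules. The gap is confined to operations that end without an implant.

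**Step 3. Possible size.** The plan gives no sample size, abandonment rate or adverse-event rate, so there is no figure to reproduce. Everything below is assumed.

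With n operations started in a group and abandonment rate a, the expected number unseen is n × a, and the chance of at least one is 1 − (1 − a)^n:

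| n started | expected unseen, a = 0.5% to 2% | chance of at least one |
|---|---|---|
| 50 | 0.25 to 1 | 22% to 64% |
| 100 | 0.5 to 2 | 39% to 87% |
| 200 | 1 to 4 | 63% to 98% |

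If c is the event rate among completed operations, the rate per attempted operation is a + (1 − a) × c. With a = 1% and c = 1% it is 0.01 + 0.99 × 0.01 = 1.99%, while the study would see 1%. Over a = 0.5% to 2% and c = 1% to 2%, it runs from 0.005 + 0.995 × 0.01 = 1.5% to 0.02 + 0.98 × 0.02 = 3.96%.

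**Step 4. One group with exact limits.** Suppose 150 operations started, 3 abandoned and no event in the other 147. The plan would report 0/147, with a 95% upper limit of 1 − 0.025^(1/147) = 2.5%. Per attempted operation the result is 3/150 = 2.0%, with Clopper-Pearson limits of 0.4% to 5.7%. The intervals overlap and 2.0% lies inside the first, so this shows a lost signal in one group, not a reversed conclusion.

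**Step 5. Between groups.** If both groups have the same c, the visible difference is zero and the true difference per attempted operation is (a1 − a2) × (1 − c). With c = 1%, a1 = 2% and a2 = 0.5%, that is 0.015 × 0.99 = 1.485 percentage points. Exchanging a1 and a2 reverses the sign, and a1 = a2 gives zero. The documents do not say which applies.

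**The case against.** **The criterion may only name the procedure.** Its mention of the ICL type suggests that it is there to separate ICL from other lenses and operations, and section 3.3 defines the population by purpose of attendance. This is a fair reading of the intent. It does not rescue the plan, because the group definitions independently require an implanted lens. At the least, the sections need reconciling.

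**Eligibility is written per participant, not per eye.** A patient with one implanted and one abandoned eye is not clearly excluded. That stands: the text leaves the case open, and the abandoned eye would still have no group.

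**Little of the study is touched.** The primary outcome is unaided acuity, which makes sense only in implanted eyes, as do the planned endothelial and pressure comparisons. The number of missing operations may be zero. This stands, and it limits the severity.

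**Stronger readings are not supported.** A reader might infer from section 6 that abandoned operations are more likely without dispersive OVD, so that the reduced group is bound to look too safe. Section 6 describes where the product has been used; it does not say what fails without it. A reader might also infer that serious intraoperative events as a class go uncounted. Only those that end without an implant do.

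**Conclusion.** The point holds in a limited form. Read together, the Inclusion Criteria and the group definitions restrict the cohort to completed implantations, in conflict with section 3.3. Operations started and ended without an implant are counted in neither group, so the intraoperative failure rate per attempted operation cannot be estimated for either technique. For a study whose stated question is safety and suitability, that is a real gap.

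The size and direction of any bias are unknown. The figures in the working depend on assumed group sizes and rates; they show that a few unseen cases are plausible in a series of ordinary size, not that any occurred. Severity is moderate and confined to the adverse-event secondary outcome. The acuity, pressure and endothelial analyses are properly carried out in implanted eyes.

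**What to change.** 1. Reconcile section 3.3 with the Inclusion Criteria by defining a safety cohort as all ICL operations started, whether or not a lens was left in the eye. State that this applies per operated eye.
2. Reword both group definitions in section 3.6 to the technique in use at the start of the operation. This also settles where a case that changed technique during surgery is counted.
3. For the adverse-event outcome only, exempt uncompleted operations from the two-visit criterion, the incomplete-data exclusion and section 3.7.
4. Identify these cases from the hospital records already screened under section 3.4 and the operative notes already read under section 3.5. The documents mention no operating log; use one if it exists.
5. Report *implantation not completed* by group, as a count over operations started with exact 95% confidence limits, or state that there were none.
6. Keep the acuity, pressure and endothelial analyses in implanted eyes.

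All of these changes are needed together, since each rule alone can keep the cases out. The cost is a few reworded sentences, a small amount of extra record review and a possibly less favourable event rate. If the search finds no such operation, one sentence saying so strengthens the safety report.

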## **3.4 Identification and Recruitment of Participants**

Potential participants will be identified by screening of all medical records from the above hospital regardless of the time of the surgery.

Study investigators will identify study participants individually after screening of medical records.

Since this study is retrospective, initial surgery consent was considered as the participant consent for the study.

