## **3.5 Study Interventions / Procedures**

After enrolment, the record of each participant is examined meticulously for completeness of preoperative and postoperative data pertaining to study including:

Patient age and gender, date of the procedure and its operative notes including laterality and surgical steps.

preoperative and postoperative assessments such as uncorrected and best corrected visual acuity, refractive error quantification both objectively utilizing an autorefractometer autorefractor Nidek ARK 1 (Nidek Inc, Gamagori, Japan) and subjectively as manifest refraction, clinical slit-lamp examination notes, intraocular pressure with air puff tonometers, AC depth assessment by Pentacam Scheimpflug (Oculus Optikgeräte GmbH Inc., Wetzlar, Germany), specular microscopy study of corneal endothelial cells (endothelial cell density (ECD), coefficient of variation (CV) and hexagonality) using Topcon SP-1p Specular Microscope (Topcon Corporation, Tokyo, Japan),

Typically, there is a preoperative visit and multiple postoperative visits extending over the period of 1-2 years after the procedure.

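### Lens model, toric or spherical type, lens power and intended refraction are not among the named data, so a lens or target difference between the preference-formed groups could be read as an OVD effect on unaided acuity

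*Combined protocol and SAP*

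**What the plan says.** - **Eligibility.** Section 3.3.1.1 requires only "Phakic intraocular lens implantation was performed (ICL type". It sets no model, type or power.
- **Period.** Section 3.4 finds participants by "screening of all medical records from the above hospital regardless of the time of the surgery", so nothing confines the cohort to one lens generation. The Background names one model, the V4c EVO, and says it "has demonstrated effectiveness and an excellent safety profile with more than one million ICL implants had already been performed globally", but no criterion limits the study to it.
- **Group formation.** Section 3.3 says "the initial group allocation occurred before the commencement of the study on the basis of surgeon and patient preference".
- **Outcomes.** Section 3.6 states "There is one primary outcome of interest which is the unaided visual acuity after the surgery", and adds "several secondary outcomes including postoperative intraocular pressure", specular microscopy and adverse events.
- **Data.** The surgical items in section 3.5 are the "date of the procedure and its operative notes including laterality and surgical steps". The section also lists unaided and best corrected acuity, objective and manifest refraction before and after surgery, slit-lamp findings, IOP, anterior chamber depth and specular microscopy. Section 3.7 treats this list as the definition of the data set. Lens model, toric or spherical type, lens power and intended refraction are not named.
- **Analysis.** Section 4.2 compares the groups on every section 3.5 parameter by unpaired t test or Mann-Whitney test, chosen after normality testing, or by chi-squared test. No adjustment, matching or stratification is planned.

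**The concern.** Unaided acuity after an ICL reflects the residual refraction, which depends on the lens implanted and the refraction aimed for. An eye deliberately left myopic (conceivable with eligibility up to age 55), or one with cylinder left behind a spherical lens, counts as a poor primary result even when surgery did what was intended.

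The OVD technique was chosen, not assigned. A surgeon or period that favoured one technique may also have favoured certain lenses or targets. If so, the unadjusted comparison mixes the two and could show a false acuity difference or hide a real one. Intended residuals that are evenly spread do not bias the comparison, but they add noise to the only primary outcome.

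Adjusting for the listed preoperative variables would not settle this, because the lens and the target are not among them.

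**Working it through.** The plan states no sample size, SD, effect size or power (section 4.1), so there is no figure of its own to reproduce. What follows is an illustration.

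**Inputs**
- From the documents: two-group comparison, t or Mann-Whitney after normality testing, P < 0.05 (section 4.2).
- Assumed: two-sided testing; acuity in logMAR with SD 0.10; intended-residual eyes 0.30 logMAR worse; 50 or 100 independent eyes per group; no true technique effect unless stated; Shapiro-Wilk at 5% in each group, with Mann-Whitney used if either group fails.

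**Step 1: false difference.** Bias = 0.30 × (p1 − p2).
- 15% v 5%: 0.30 × 0.10 = 0.03 logMAR.
- 10% v 5%: 0.30 × 0.05 = 0.015 logMAR.

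**Step 2: t test in closed form.** The variance in a group is 0.10² + 0.30² × p(1 − p).
- p = 15%: 0.01 + 0.09 × 0.1275 = 0.021475.
- p = 5%: 0.01 + 0.09 × 0.0475 = 0.014275.
- At 100 per group, SE = √((0.021475 + 0.014275)/100) = 0.0189, and bias/SE = 0.03/0.0189 = 1.59.
- Rejection probability = 1 − Φ(1.96 − 1.59) + Φ(−1.96 − 1.59), about 35%.

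**Step 3: the test the plan would use.** The mixture is skewed. In simulation at 100 per group, normality is rejected in at least one group in about 96% of studies, so Mann-Whitney is nearly always chosen. It is less sensitive to a minority of poor values, so the relevant rates are below the 35%.

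| Intended-residual eyes | Eyes per group | False positives under the plan's test choice |
|---|---|---|
| 15% v 5% | 100 | about 24% (22% to 24% over repeat runs) |
| 15% v 5% | 50 | about 14% (14% to 15%) |
| 10% v 5% | 100 | about 10% (9% to 10%) |
| none in either | 100 | about 5% |

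**Step 4: balanced groups.** With 10% such eyes in both groups there is no bias. Power for a real 0.04 logMAR difference at 100 per group falls from about 79% to about 62% under the plan's test choice. For the t test alone, in closed form:
- Without such eyes, SE = √(0.02/100) = 0.01414 and power is Φ(0.04/0.01414 − 1.96), about 81%.
- With them, the variance is 0.01 + 0.09 × 0.09 = 0.0181 per group, SE = √(0.0362/100) = 0.0190, and power is about 56% (53% to 56% with simulation).

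**Step 5: a factor of unknown size, in SD units.** This form can be applied to IOP, for which the documents give no effect by lens model. If a lens factor shifts the outcome by g SD and its prevalence differs by d, the bias is g × d. With p = 0.5 + d/2, SE = √(2(1 + g²p(1 − p))/n).

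| g | d | n = 30 | n = 50 | n = 100 |
|---|---|---|---|---|
| any | 0 | 5% | 5% | 5% |
| 0.5 | 20 points | 7% | 8% | 11% |
| 0.5 | 40 points | 12% | 16% | 28% |
| 1.0 | 40 points | 29% | 44% | 73% |

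These are false-positive rates under assumed values. Nothing in the documents says which row applies.

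**The case against.** Four stronger readings are tempting, and the documents support none of them fully.

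**That lens and target are not extracted at all.** Section 3.5 names the operative notes as a source and introduces its list as non-exhaustive. Lens details may well be recoverable from the notes. What the plan lacks is a commitment to record them.

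**That a difference could be neither detected nor corrected.** Postoperative manifest refraction would show residual myopia or cylinder. Best corrected acuity would largely separate refractive from other loss. Section 4.2 compares both between groups, and the procedure date is a partial proxy for lens era. What survives is narrower: measured refraction cannot separate an intended residual from a missed target, and none of these variables is used to correct the primary comparison.

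**That IOP depends heavily on lens model.** The Background lists raised IOP and pupillary block as complications of ICL surgery in general, and the one mechanism it gives for an early IOP rise is retained viscoelastic. It gives no IOP figure by model. The documents also do not show that more than one model was used at this single hospital. The IOP part is a possibility only.

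**That the error is as large as the t test suggests.** The 35% false-positive rate and the power fall from 81% to between 53% and 56% apply to the t test alone, which the plan would rarely select here.

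It is also fair to say that bias needs an imbalance, and none is documented. That stands. But without the lens and target data the plan cannot show balance either.

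**Conclusion.** The point holds in a limited form. Any ICL from any date is eligible, the groups arose from preference, the tests are unadjusted, and the four items that describe the lens and its target are not named for extraction. For unaided acuity, dependence on the intended residual follows by definition. A lens or target difference could therefore be read as an OVD effect, or mask one.

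On the assumed inputs, false positives are about 10% to 24% at 100 eyes per group, depending on the imbalance, and about 14% at 50 per group with the larger imbalance. With balanced groups the cost is power, about 79% down to 62%. These sizes rest on the assumed SD, acuity loss and shares of affected eyes, which the documents do not supply. For IOP no size can be stated. This is a worthwhile improvement to the data set and analysis, not evidence that the comparison is already biased.

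**What to change.** 1. Add four items to section 3.5: ICL model, toric or spherical type, lens power and intended postoperative refraction. Take them from existing operative notes, lens labels or calculation sheets.
2. Exempt these items from the section 3.7 rule, so that a missing target does not remove a participant from the study.
3. Tabulate all four by group, including how often each is missing.
4. Compare primary unaided acuity in eyes with recorded emmetropic intent, stratified by or adjusted for toric or spherical type, and report the all-eyes comparison alongside it.
5. If more than one ICL model was used, stratify the IOP and adverse-event comparisons by model.

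**Cost.** Four more extraction columns and one further comparison, all from records already held. Eyes without a recorded target leave the emmetropic-intent comparison. The loss of precision depends on how often the target was recorded, which is unknown; reporting all eyes alongside shows how much the restriction matters.
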